3.2.9.4 Vital signs

Vital sign assessments will be performed in order to characterize basic body function. The parameters collected are weight (kg), body temperature (°C), pulse rate (beats per minute), systolic and diastolic blood pressure (mmHg).

Clinically notable elevated values are defined as:

- Systolic BP: \geq 160 mmHg and an increase \geq 20 mmHg from baseline
- Diastolic BP: \geq 100 mmHg and an increase \geq 15 mmHg from baseline.
- Body temperature: \geq 39.1°C
- Weight: increase from baseline of \geq 10%
- Pulse rate: \geq 120 bpm with increase from baseline of \geq 15 bpm

Clinically notable below normal values are defined as:

- Systolic BP: \leq 90 mmHg and a decrease \geq 20 mmHg from baseline
- Diastolic BP: \leq 50 mmHg and a decrease \geq 15 mmHg from baseline
- Body temperature: \leq 35°C
- Weight: decrease from baseline of \geq 10%
- Pulse rate: \leq 50 bpm with decrease from baseline of \geq 15 bpm

Vital signs shift table based on values classified as notable low, normal, notable high or notable (high and low) at baseline and worst post-baseline will be produced for pulse rate, diastolic BP and systolic BP.

Descriptive statistics will be tabulated for baseline and change from baseline to worst post-baseline value for each vital sign measurement.

Patients with at least one clinically notable vital sign abnormalities will be listed. All vital sign assessments will be listed by patient and vital sign parameter.

In the listings, clinically notable values will also be flagged.

WHO performance status

ECOG performance scale is provided in [Table 3-2](#) and is used to assess physical health of patients, ranging from 0 (most active) to 5 (dead):

Table 3-3 WHO performance scale

Score	Performance Status
0	Fully active, able to carry on all pre-disease performance without restriction
1	Restricted in physically strenuous activity but ambulatory and able to carry out work of a light or sedentary nature, e.g. light house work, office work
2	Ambulatory and capable of all self-care but unable to carry out any work activities. Up and about more than 50% of waking hours
3	Capable of only limited self-care, confined to bed or chair more than 50% of waking hours
4	Completely disabled. Cannot carry on any self-care. Totally confined to bed or chair
5	Dead

Shift tables of WHO performance status at baseline to worst post-baseline WHO status by score will be presented; shift tables of ECOG performance status at baseline to best post-baseline ECOG status by score will also be provided. WHO performance status at each time point will be listed.

3.2.10 Efficacy evaluation

All efficacy analyses will be performed based on the FAS, unless otherwise specified.

3.2.10.1 Overall response rate – key secondary objective

The key secondary objective in this study is to evaluate anti-tumor activity of LDK378 in term of ORR as assessed by the investigator per RECIST 1.1. ORR is defined as the proportion of patients with a best overall confirmed complete response (CR) or partial response (PR) per RECIST 1.1.

Best overall response

The best overall response will be assessed based on reported lesion responses at different evaluation time points. Both CR and PR must be confirmed by repeat assessments performed not less than 4 weeks after the criteria for response are first met. The next scheduled assessment may be used for purposes of confirmation of response. Best overall confirmed response for each patient is determined from the sequence of overall (lesion) responses according to the following rules:

- CR = at least two determinations of CR at least 4 weeks apart before progression.

- PR = at least two determinations of PR or better at least 4 weeks apart before progression (and not qualifying for a CR).
- SD = at least one SD assessment (or better) > 6 weeks after start of treatment (and not qualifying for CR or PR).
- PD = progression ≤ 12 weeks after start of treatment (and not qualifying for CR, PR or SD).
- UNK = all other cases (i.e. not qualifying for confirmed CR or PR and without SD after more than 6 weeks or progression within the first 12 weeks)

Confirmed partial or complete responses reported prior to any additional anticancer therapy will be considered as responses in the calculation of the ORR irrespective of the number of missed assessments before response. Unconfirmed PR and unconfirmed CR are considered as stable disease (SD) if > 6 weeks after start of treatment, otherwise considered as unknown. Patients who are of unknown clinical response will be treated as non-responders.

Only tumor assessments performed before the start of any further anti-neoplastic therapies (i.e. any additional secondary anti-neoplastic therapy or anti-cancer surgery) will be considered in the assessment of best overall response. Further anti-neoplastic therapies will be identified via protocol deviations or from the data collected on 'Anti-neoplastic therapies since discontinuation of study drug' as appropriate. Clinical deterioration will not be considered as documented disease progression. Patients with best overall response 'unknown' will be summarized by reason for having unknown status. The following reasons will be used:

- No valid post-baseline assessment
- All post-baseline assessments have overall response UNK
- New anti-neoplastic therapy started before first post-baseline assessment
- Stable disease (SD) too early (≤ 6 weeks after start date of study drug)
- PD too late (> 12 weeks after start date of study drug)

Special (and rare) cases where best overall response is 'unknown' due to both early SD and late PD will be classified as 'SD too early'.

Patients who have disease progression and continue to receive treatment after progression will qualify for progressive disease at the time of progression and will be counted as PD in ORR and other efficacy calculations.

The analysis of ORR will be performed on the FAS. The ORR will be estimated and the 95% confidence interval (CI) based on the exact binomial distribution will be provided.

Supportive Analyses

The supportive analyses will be based on BIRC assessment of ORR for FAS. The analysis of ORR will also be repeated using PPS.

Concordance/discordance of best overall response between BIRC and investigator assessments will be summarized and also presented in detail by listings. Waterfall plots representing the best percentage change from baseline in the sum of the tumor measured diameters for target lesions will be produced.

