6.3.1.5 Palliative radiotherapy and surgery

Local radiotherapy for analgesic purposes or for lytic lesions at risk of fracture may be carried out if required. If palliative radiotherapy is initiated after start of study treatment, the reason for its use must be clearly documented and progression as per RECIST 1.1 must be assessed and documented.

Patients who develop progressive disease but are still deriving clinical benefit from ceritinib therapy, as determined by the Investigator may undergo radiotherapy and/or surgical resection as palliative localized therapy to treat metastatic lesions. Ceritinib should be held for at least 4 days prior to radiotherapy and at least 1 day prior to any surgery. Ceritinib may be resumed ≥ 3 days after completing radiotherapy or minor surgery, and ≥ 2 weeks after major surgery.

[figure not shown]

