6.3.2 Prohibited concomitant therapy

6.3.2.1 Other anticancer therapy

Anticancer therapy (chemotherapy, targeted therapy, biologic therapy or radiation therapy (except palliative radiotherapy as described in [Section 6.3.1.5](#)), and anti-cancer surgery) other than the study treatment must not be given to patients while they are enrolled in the treatment portion of the trial. If such agents are required then the patient must be permanently discontinued from the treatment portion of the study.

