7.2.1.1 Baseline assessments

Tumor evaluation will be performed at baseline within 28 days of, and prior to study treatment.

Contrast-enhanced CT (or MRI) should preferably be performed using a 5 mm slice thickness with a contiguous reconstruction algorithm. CT/MRI scan slice thickness should not exceed 8 mm cuts using a contiguous reconstruction algorithm.

Required conditions for tumor assessment at baseline

- Patients must have measurable disease as per RECIST v1.1 ([Appendix 2](#)). Measurable lesions include lytic or mixed (lytic + blastic) bone lesions with an identifiable soft tissue component that meets the measurability criteria per RECIST v1.1 (Appendix 2).
- Patients with only non-measurable lesions are not eligible.
- If the measurable disease is restricted to a solitary lesion, its neoplastic nature should be confirmed by cytology/histology.
- Any potentially measurable lesion that has been previously treated with radiotherapy should be considered as a non-measurable lesion. However, if a lesion previously treated with radiotherapy has clearly progressed since the radiotherapy, it can be considered as a measurable lesion.
- All measurable lesions up to a maximum of 5 nodal and/or non-nodal lesions in total (and a maximum of 2 lesions per organ), representative of all involved organs, should be identified as target lesions and recorded and measured at baseline.

Required image assessments for tumor assessment at baseline

The following assessments will be performed:

- Computed Tomography (CT) or Magnetic Resonance Imaging (MRI) of chest and abdomen.
 - The preferred radiologic technique is CT with intravenous (i.v.) contrast. If a patient is known to have a contraindication to CT contrast media or develops a contraindication during the trial, a non-contrast CT of the chest (MRI is not recommended due to respiratory artifacts) plus a contrast-enhanced MRI (if possible) of the abdomen should be performed.

- A whole body bone scan according to institutional guidelines (e.g. Tc-99 bone scan, whole body bone MRI, FDG-PET or sodium fluoride positron emission tomography (NaF PET)).
- Localized CT, MRI or X-rays of all skeletal lesions identified on the screening bone scan, which are not visible on the chest and abdomen CT/MRI (and pelvis CT/MRI if applicable)

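### The best-overall-response rule does not detect permitted radiotherapy before progression, so shrinkage of an irradiated target lesion can count toward ORR and the waterfall plot

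*SAP*

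**What the plan says.** **The response rule.** SAP 3.2.10.1 restricts best overall response to assessments made before "any further anti-neoplastic therapies (i.e. any additional secondary anti-neoplastic therapy or anti-cancer surgery"). For finding such therapy, it says: "Further anti-neoplastic therapies will be identified via protocol deviations or from the data collected on" the form for therapies since discontinuation of study drug.

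**What is permitted on treatment.** Protocol 6.3.1.5: "Local radiotherapy for analgesic purposes or for lytic lesions at risk of fracture may be carried out if required". If this happens after the start of study treatment, "the reason for its use must be clearly documented and progression as per RECIST 1.1 must be assessed and documented". Nothing confines it to non-target lesions. Protocol 6.3.2.1 lists the therapies that may not be given on treatment, among them "radiation therapy (except palliative radiotherapy as described in" 6.3.1.5).

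**Which lesions can be targets.** Protocol 7.2.1.1: "Measurable lesions include lytic or mixed (lytic + blastic) bone lesions with an identifiable soft tissue component that meets the measurability criteria". The same section, on radiotherapy before baseline: "Any potentially measurable lesion that has been previously treated with radiotherapy should be considered as a non-measurable lesion", unless the lesion has clearly progressed since.

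**Neighboring rules.** Protocol Appendix 2 (14.2.3.1) says that assessments after alternative cancer therapy taken on study are ordinarily left out of best overall response. SAP 3.2.10.2 censors PFS when a patient has had any anticancer therapy apart from study drug (row F of the PFS/DOR outcome table), and DOR follows PFS.

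**The concern.** The Protocol distrusts a lesion irradiated before baseline: it may be a target only if it has since grown. No counterpart exists once treatment has begun. The lytic lesions that may be irradiated are a kind that can be chosen as targets, and the SAP's two detection sources look elsewhere. ORR is the key secondary endpoint of an open-label, single-arm study, is assessed by the investigator, and is meant to support registration in China (Protocol 2.1). There is no control arm in which shrinkage from local treatment would also appear, so any such shrinkage is credited to LDK378.

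**Working it through.** **1. Does permitted radiotherapy reach either detection source?**
- *Protocol deviations:* no. Because of the exception in Protocol 6.3.2.1, giving it is not a deviation.
- *Form for therapies since discontinuation:* no. The patient is still on study drug.
- *Where it may be recorded:* Protocol 6.3 sends procedures from 28 days before first dose to 30 days after last dose to the Surgical and Medical Procedures eCRF. SAP 3.2.6 summarizes that page, but SAP 3.2.10.1 does not use it.

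**2. Does a later rule stop the lesion from counting?** In Appendix 2, target response becomes unknown only when a lesion is not assessed or the method changes (Table 14-5). Overall response follows from that (Table 14-7). PR is a 30% fall in the target sum, whatever the cause. The waterfall algorithm in SAP 4.2.1 has no radiotherapy exclusion. Independent review is supportive, and no stated rule tells it to treat irradiated lesions differently.

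**3. Which radiotherapy matters?** Only radiotherapy given without PD. Appendix 2 drops assessments after progression from best overall response, so the post-PD route in 6.3.1.5 cannot create a response. For ORR it must also precede confirmation, which requires a second assessment at least 4 weeks later.

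**4. How much shrinkage is needed?** Let *s* be the irradiated lesion's share of the baseline target sum and *r* its shrinkage, with the other targets unchanged. PR needs s × r ≥ 30%, so r ≥ 30/s.

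| Share s | Shrinkage needed |
|---|---|
| 30% | 100% |
| 40% | 75% |
| 50% | 60% |
| 60% | 50% |
| 100% (single target) | 30% |

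Partial drug response lowers the bar. With s = 50% and the other targets down 20%, those lesions supply 0.5 × 20 = 10 points, and the irradiated lesion needs (30 − 10)/0.5 = 40%.

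**5. Effect on ORR.** The plan's own figure first (Protocol 10.10, SAP 3.4): for 45/100 the exact 90% limits are the 5% quantile of Beta(45, 56) and the 95% quantile of Beta(46, 55). These give 36.52% and 53.71%, matching the stated 36.5% to 53.7%.

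The Amendment 3 rationale gives 103 treated patients, which is the FAS denominator. Each responder reclassified moves ORR by 1/103 = 0.97 points. Starting from 46/103 (0.45 × 103 = 46.35, rounded), with the exact 95% interval planned for ORR:

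| Responders removed (assumed) | ORR | Exact 95% CI |
|---|---|---|
| 0 | 44.7% | 34.9 to 54.8 |
| 1 | 43.7% | 33.9 to 53.8 |
| 2 | 42.7% | 33.0 to 52.8 |
| 3 | 41.7% | 32.1 to 51.9 |
| 5 | 39.8% | 30.3 to 49.9 |

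The documents give no count of such patients, so the left column is an assumption.

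**6. Why the obvious repair fails.** One might set every later response to unknown unless PD. SAP 4.2.1 treats an unknown assessment as a missing one and sets the two-missing threshold at 2 × 8 + 2 = 18 weeks. Take a last adequate scan, unknown scans 8 and 16 weeks later, and PD at 24 weeks. Since 24 > 18, row C2 censors a true progression at the last scan before radiotherapy.

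**The case against.** The best contrary case is that the documents' vocabulary already covers radiotherapy. SAP 3.2.2 divides prior anti-neoplastic therapy into medications, radiotherapy and surgery. SAP 3.2.7 speaks of antineoplastic radiotherapy after discontinuation. The exception in Protocol 6.3.2.1 can be read as lifting a prohibition without changing what radiotherapy is. The Appendix 2 default and the PFS wording are broad enough to include it.

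This stands as far as it goes. A reader might infer that the plan declares palliative radiotherapy not to be new therapy, or declares irradiated targets evaluable. No text says either. But none of the broad passages names on-treatment radiotherapy or adds a source that would find it. The one operational rule for best overall response names two sources, and both miss it. Followed as written, that rule departs from the Appendix 2 default.

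A reader might also infer that DOR and DCR are inflated to the same degree. For DOR, the PFS wording on its face may censor at radiotherapy, so the direction is unclear. DCR needs only SD after more than 6 weeks, so radiation shrinkage adds little. Masked progression is partly handled, because 6.3.1.5 requires RECIST progression to be assessed when radiotherapy is used.

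Finally, the window may look short: in the earlier study 86.1% of responders had responded within 12 weeks (Protocol 1.2.1.2.2). Confirmation lengthens it. With 8-weekly scans, a response first seen at week 8 is confirmed at week 16 if the next scheduled scan is used.

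**Conclusion.** The gap is real and should be closed. SAP 3.2.10.1 does not detect permitted radiotherapy before progression, and nothing later in the plan prevents an irradiated target lesion from contributing to a confirmed response or to the waterfall plot. The section also conflicts with Appendix 2 and with the broader PFS wording.

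The effect on ORR can only be upward and is probably small. The figure of about 1 point is a ceiling per patient. It applies only if the lesion is a target, radiotherapy precedes confirmation, the patient would otherwise be a non-responder, the 30% fall depends on that lesion and is confirmed, and there is no new lesion or non-target progression. It would be wrong to assign 1 point to every irradiated patient. ORR carries no formal test (Protocol 10.10), and the primary PK and safety objectives are untouched.

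**What to change.** 1. **SAP 3.2.10.1, detection.** Add on-treatment radiotherapy recorded on the Surgical and Medical Procedures eCRF as a third source. Protocol 6.3 does not name radiotherapy among the procedures, so first confirm that the page captures its date and site.
2. **SAP 3.2.10.1 and the waterfall rules in 4.2.1.** State that assessments after radiotherapy to a target lesion do not count toward establishing or confirming CR/PR, or toward the best percentage change. A response confirmed before radiotherapy stands.
3. **SAP 4.2.1, missing assessments.** State that these assessments are not missing adequate assessments, so later PD or death is not censored under row C2 for this reason.
4. **SAP 3.2.10.2 and row F.** Align the new-therapy wording for PFS and DOR with this rule, saying explicitly how permitted palliative radiotherapy is handled.

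The cost is SAP wording, one programming flag and possibly a slightly lower ORR. No new data collection is needed if the eCRF page already holds date and site.

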3.2.10.2 Other secondary efficacy objectives

The other secondary efficacy objectives are:

- To evaluate DOR, DCR, TTR, OIRR and PFS both by investigator assessment and BIRC assessment
- To evaluate ORR and OIRR by BIRC
- To evaluate OS

Duration of Response

Among patients with a confirmed response (PR or CR) per RECIST 1.1 by investigator, DOR is defined as the time from first documented response (PR or CR) to the date of first documented disease progression or death due to any cause. If a patient has not had an event, DOR is censored at the date of last adequate tumor assessment.

The censoring and event date options to be considered for the DOR analysis follow those for PFS below.

DOR will be described in tabular and graphical format using Kaplan-Meier methods including estimated median (in months) with 95% CI, 25th and 75th percentiles ([Brookmeyer and Crowley 1982](#), [Klein and Moeschberger 1997](#)) and Kaplan-Meier estimated probabilities with corresponding 95% CIs ([Kalbfleisch and Prentice 1980](#)) at several time points (including at least 3, 6, 9, 12, 15 and 18 months).

Refer to [Section 4.2.3.3](#) for further details regarding derivation of Kaplan –Meier estimates.

Disease control rate

DCR, defined as the proportion of patients with best overall response of CR, PR, SD, or Non-CR/Non-PD per RECIST 1.1 by investigator will be estimated and the 95% CI ([Clopper & Pearson, 1934](#)) based on the exact binomial distribution will be provided.

Time to response

Time to overall response of CR or PR (TTR) is defined as the time from start of study drug to first documented response (CR or PR, which must be confirmed subsequently) for patients with a confirmed CR or PR.

TTR will be summarized in 2-month intervals using descriptive statistics. The analysis will be performed based on investigator assessment.

Progression-free survival

PFS is defined as the time from the date of first dose of study drug to the date of the first documented disease progression per RECIST 1.1 by investigator, or death due to any cause.

If a patient has not progressed or is not known to have died at the date of analysis cut-off or has received any anticancer therapy other than study drug, PFS will be censored at the date of the last adequate tumor evaluation before the cut-off date or before the start of the new anticancer therapy date, whichever is earlier. Clinical deterioration will not be considered as a qualifying

event for progression. Refer to [Table 3-3](#) for censoring and event date options and outcomes for PFS.

In particular, PFS will be censored at the last adequate tumor assessment if one of the following occurs: absence of event; the event occurred after a new anticancer therapy is given; the event occurred after two or more missing tumor assessments (see [Section 4.2.1](#)). See also [Section 4.2.1](#) describing the special case of a missing baseline tumor assessment.

PFS will be described in tabular and graphical format using Kaplan-Meier methods as described for DOR, including estimated median (in months) with 95% CI, 25th and 75th percentiles and Kaplan-Meier estimated probabilities with corresponding 95% CIs at several time points (including at least 3, 6, 12, 18 and 24 months). Censoring reasons will also be summarized (see [Section 4.2.1](#))

Table 3-4 Outcome and event dates for PFS and DOR analyses

Situation	Date	Outcome
A No baseline assessment	Date of first dose of study drug ^a	Censored
B Progression at or before next scheduled Assessment	Date of progression	Progressed
C1 Progression or death after exactly one missing assessment	Date of progression (or death)	Progressed
C2 Progression or death after two or more missing assessments	Date of last adequate assessment	Censored
D No progression	Date of last adequate assessment	Censored
E Treatment discontinuation due to 'Disease progression' without documented progression, i.e. clinical progression based on investigator claim	N/A	Information ignored. Outcome derived based on radiology data only.
F New anticancer therapy given	Date of last adequate assessment	Censored

^aThe rare exception to this is if the patient dies no later than the time of the second scheduled assessment as defined in the protocol in which case this is a PFS event at the date of death

In addition, summary tables of PFS by brain metastasis at baseline status (presence vs. absence) will be generated by investigator and BIRC assessment respectively.

Overall survival

OS is defined as the time from the first dose of study drug to the date of death due to any cause. If the patient is alive at the date of the analysis cut-off or lost to follow-up, then OS will be censored at the last contact date prior to data cutoff date (see [Section 4.1.4](#) for further details on derivation of last contact date).

OS will be described in tabular and graphical format using Kaplan-Meier methods as described for DOR, including estimated median (in months) with 95% CI, 25th and 75th percentiles and Kaplan-Meier estimated probabilities with corresponding 95% CIs at several time points

(including at least 3, 6, 12, 18 and 24 months). Censoring reasons ('Alive' or 'Lost to follow-up') will be summarized. Patients not known to have died will be censored for 'Lost to follow-up' if the time between their last contact date and the analysis cut-off date is longer than four cycles plus 2 weeks, i.e., 18 weeks for this study.

Overall intracranial response rate

OIRR is calculated based on response assessments in the brain for patients 1) having both measurable and/or non-measurable brain metastases at baseline (i.e. at least one target/and or non-target lesion in the brain); 2) having measurable brain metastases at baseline (i.e., at least one target lesion in the brain). OIRR is defined as the proportion of patients with a best overall confirmed response of CR or PR in the brain, as assessed per RECIST 1.1 by the investigator.

OIRR will be estimated and the 95% CI based on the exact binomial distribution will be provided. For details on the OIRR calculations see [section 4.2.4](#).

The following analyses will be performed:

- Best overall intracranial response per investigator assessment (Full analysis set - Patients with measurable and/or non-measurable disease in the brain at baseline as per investigator review)
- Best overall intracranial response per investigator assessment (Full analysis set – patients with measurable disease in the brain at baseline as per investigator review)

Supportive analyses

DOT, DCR, TTR, PFS and OIRR will also be assessed by BIRC using the same analytical conventions as analysis by investigator assessment and serve as the basis of supportive analysis.

Duration of Follow-up and Gap Analyses

Follow-up in the study will be summarized using the following methods to provide a comprehensive assessment of follow-up for all patients.

Summary of duration between start date of study drug and cut-off date, and follow-up times for PFS/OS, are defined as follows:

- Duration between start date of study drug and data cut-off date = (Cut-off date – Start date of study drug + 1) / 30.4375 (months).
- Follow-up time = (Date of event or censoring – Start date of study drug + 1) / 30.4375 (months) regardless of censoring. Date of censoring is defined as the last adequate tumor assessment date for PFS or last contact date (when the patient is known as alive) for OS.

Summaries will also be tabulated for the gap time for PFS/OS follow-up compared to the cutoff date. Gap analysis is the summary of gap time (months) for PFS/OS follow-up as compared to cut-off date. Gap time for PFS/OS is defined as follows

- For patients who are censored regardless of follow-up status,
Gap time = (data cut-off date – censoring date)/30.4375 (months).

- For patients who completed study phase or prematurely discontinued from the study due to certain reasons e.g. withdraw consent, lost to follow-up,

[figure not shown]
Gap time = (min(data cut-off date, study discontinuation date)- censoring date)/30.4375 (months).

- For patients who are censored but still in follow-up,
Gap time = (data cut-off date – censoring date)/30.4375 (months).

Quartiles, minimum and maximum as well as the frequency count and percentage of patients in each of <4, 4-<8, 8-<12, 12-<18, \geq 18 months will be reported for PFS and OS gap time for patients who were censored.

All summaries will be reported in months (see Section 4.1.5). The calculations for PFS will be based on investigator assessment. Date of censoring is the same as defined for the PFS and OS analysis.

